7.7 Concomitant Therapy

All treatments other than ozanimod being taken by the participants on entry to the study or at any time during the study, including through the Safety Follow-up Visit, are regarded as concomitant medications and must be documented on the appropriate section of the eCRF. Complete history of previous treatments for CD must be documented.

NOTE: Prior to randomization (Day), all prior medications for the management of CD should be recorded on the prior CD medications eCRF. After randomization (Day , medications for the management of CD should be recorded on the concomitant medications eCRF (this eCRF also captures ongoing CD medications). All prior medications (including over-the-counter medications) administered 30 days prior to the date of informed consent/assent and any concomitant therapy administered to the participant during the course of the study until after the final dose of IP will be recorded. Additionally, all diagnostic, therapeutic, or surgical procedures relating to CD should be recorded. Any medication that is considered necessary for the participant's health (including enteral nutrition) and that is not expected to interfere with the evaluation of or interact with IP may continue during the study.

Participants who are receiving oral corticosteroids at Screening must keep their prescribed dosage steady at least through after which the dose should be tapered as described in Section 7.7.1. Oral 5-ASA or oral corticosteroids should not be started in participants who are not receiving them. Participants receiving 5-ASA must keep their prescribed dosage steady at least through and should maintain a stable dose through Week 64.

It is also advised, if possible, to keep the prescribed dose of pre- and/or probiotic supplements steady and to avoid initiating treatment with pre- and/or probiotic supplements through Week 64.

Concomitant treatment with medications listed in Section 7.7.2 is not allowed during the study.

The decision to temporarily interrupt dosing for treatment of an intercurrent medical condition, or for major surgery that could present an unreasonable risk to the participant, remains the responsibility of the treating physician, which will not be delayed or refused by the Sponsor. Prior to interruption of dosing, the investigator may contact the Medical Monitor and forward appropriate supporting documents for review and discussion. The investigator will report the action taken with IP. The Medical Monitor should be contacted to discuss treatment reinitiation. See Section 8 for permanent discontinuation of IP.

Administration of concomitant medications must be reported in the appropriate section of the eCRF along with dosage information, dates of administration, and reasons for use. For medications with a single active ingredient, generic names for concomitant medication should be used, if possible. For combination products, brand names should be used. The total daily dose should be filled in whenever possible.

In addition, SARS-CoV-2 vaccines administered any time prior to or during the study must be documented, including manufacturer details and dates for each dose. Histories of all other prior medications taken during the 30 days prior to the date of informed consent/assent must also be documented.

If vaccination for SARS-CoV-2 is pursued, ideally randomization (Day) should occur after the full dosing schedule has been administered and after resolution of any acute reactions (eg, reactions occurring within 24 hours of vaccine administration). If a participant has received a SARS-CoV-2 vaccination, vaccine details (eg, manufacturer and dose number) should be recorded on the concomitant medication page, if given during the study, or the past history page, if given prior to enrollment.

7.7.1 Steroid Taper

Steroid tapering can start as early as after Week 12 and have it completed within 6 months after Week 12. Considerations to taper at an earlier time point for adverse events or safety concerns should first be discussed with the Clinical Trial Physician or designee. Below is the recommended tapering schedule. Modification can be made based on body weight following discussion with the Clinical Trial Physician or designee.

Participants receiving prednisone at a dose of > 10 mg/day (or equivalent) are recommended to have their dose reduced at a rate of 5 mg (or equivalent) per week until a ≤ 10 mg/day dose (or equivalent) is achieved. Participants receiving prednisone at doses of 10 mg/day (or equivalent) or have achieved a 10 mg/day dose (or equivalent) by tapering are recommended to have their dose reduced at a rate of 2.5 mg/week until the steroid is discontinued. Participants receiving oral budesonide are recommended to taper their dose at a rate of 3 mg every 3 weeks and then discontinue treatment. Participants receiving oral beclomethasone are recommended to taper their dose over a period of up to 6 weeks.

Protocol Amendment No.: 02

For participants who cannot tolerate the corticosteroid taper without recurrence of clinical symptoms of either CD or steroid withdrawal, the corticosteroid dose may be increased (up to the dose at study entry if required), but tapering should be attempted again within 2 weeks.

7.7.2 Prohibited and/or Restricted Treatments

The following medications cannot be used during the study through the Safety Follow-up Visit, unless otherwise noted to be prohibited through end of treatment only:

- Treatment with Class Ia or Class III anti-arrhythmic drugs (examples of Class Ia or Class III anti-arrhythmic drugs and additional prohibited systemic cardiac medications are provided in Table 7.7.2-1) or treatment with 2 or more agents in combination known to prolong PR interval (eg, combination of a beta blocker and a non-dihydropyridine calcium-channel blocker) are prohibited during the study unless approved by the Sponsor's representative
- Biologic therapies including but not limited to abatacept, infliximab, etanercept, adalimumab, anakinra, rituximab, vedolizumab, ustekinumab, and golimumab
- Systemic immunomodulatory agents (eg, AZA, 6-MP, cyclosporine, MTX, mycophenolate mofetil, tacrolimus, or sirolimus; small molecules [eg, upadacitinib])
- Post-baseline initation, or increase above baseline dose, of systemic corticosteroids during Induction or Maintenance. Increase in systemic corticosteroids, such as oral prednisone > 1.0 mg/kg/day for weights ≤ 40 kg, > 40 mg/day for weights > 40 kg, or equivalent during LTE.
- Any per-rectum therapy including enemas (eg, 5-ASA, corticosteroid), other than that required for endoscopy preparation (prohibited through end of treatment only)
- Any investigational drug other than the IP specified in this study
- Chronic NSAID use (prohibited through end of treatment only. Note: occasional use of NSAIDs and acetaminophen [eg, headache, arthritis, myalgias, or menstrual cramps] and aspirin as needed or up to 325 mg/day if on a stable dose at randomization [Day] is permitted.)
- Live vaccines or live attenuated vaccines are not allowed within 4 weeks prior to randomization (Day
- IVIg or plasmapheresis is not allowed within 3 months prior to randomization (Day
- Treatment with D-penicillamine, leflunomide, or thalidomide
- Treatment with natalizumab, fingolimod, etrasimod, or other S1P modulators
- Immunosuppressive agents that deplete lymphocytes
- Anti-neoplastic medications
- Monoamine oxidase inhibitors (eg, selegiline, phenelzine)
- CYP2C8 inducers (e.g. rifampicin)

For any systemic therapies for CD not mentioned above, please contact the Clinical Trial Physician or designee.

Protocol Amendment No.: 02

Table 7.7.2-1: Examples of Prohibited Cardiac Medications (Systemic Use)

Pharmaceutical Class	Example Medications
Anti-arrhythmic drugs	amiodarone, bepridil hydrochloride, disopyramide, dofetilide, dronedarone, flecainide, ibutilide, sotalol, lidocaine, procainamide, propafenone, quinidine, tocainide

The following medications should not be used between the Safety Follow-up Visit and the Safety Follow-up Visit:

- Treatment with Class Ia or Class III anti-arrhythmic drugs (examples of Class Ia or Class III anti-arrhythmic drugs and additional prohibited systemic cardiac medications are provided in Table 7.7.2-1) or treatment with 2 or more agents in combination known to prolong PR interval (eg, combination of a beta blocker and a calcium-channel blocker) are prohibited during the study unless approved by the Sponsor's representative
- Treatment with natalizumab, fingolimod, etrasimod, or other S1P modulators
- Immunosuppressive agents that deplete lymphocytes
- Monoamine oxidase inhibitors (eg, selegiline, phenelzine)
- Live vaccines or live attenuated vaccines

7.7.2.1 Imaging Restriction and Precautions

It is the local imaging facility's responsibility to determine, based on participant attributes (eg, allergy history, diabetic history, and renal status), the appropriate imaging modality and contrast regimen per imaging study. Imaging contraindications and contrast risks are to be considered in this assessment. Participants with renal insufficiency are to be assessed as to whether or not they should receive contrast and if so, which contrast agent and dose is appropriate. Please see Section 9.1.2 for details on imaging assessments for this study.

7.8 Continued Access to Study Intervention After the End of the Study

At the conclusion of the study, if the study intervention is not available as an approved treatment in the local country, participants who continue to demonstrate clinical benefit will be eligible to receive BMS-supplied study intervention per local or regional requirements. If the study treatment is not available as an approved and available treatment, study intervention will be provided via an extension of the study, a rollover study requiring approval by the responsible Health Authority and ethics committee, or through another mechanism at the discretion of BMS.

BMS reserves the right to terminate access to BMS-supplied study intervention if any of the following occur: a) the study is terminated due to safety concerns; b) the development of ozanimod is terminated for other reasons, including, but not limited to, lack of efficacy and/or not meeting the study objectives; c) the participant can obtain medication from a government-sponsored or other health program. In all cases, BMS will follow local regulations.

8 DISCONTINUATION CRITERIA

8.1 Discontinuation From Study Intervention

Participants MUST discontinue IP for any of the following reasons:

- Participant's request to stop study intervention. Participants who request to discontinue study
 intervention will remain in the study and must continue to be followed for protocol-specified
 follow-up procedures. The only exception to this is when a participant specifically withdraws
 consent for any further contact with him/her or persons previously authorized by the participant
 to provide this information.
- If a participant who does not meet enrollment criteria is inadvertently enrolled, the Clinical Trial Physician or designee must be contacted, and that participant will be withdrawn from the study if continuation is determined to be a safety risk.
- Any clinical AE, laboratory abnormality, or intercurrent illness which, in the opinion of the investigator, indicates that continued participation in the study is not in the best interest of the participant.
- Termination of the study by BMS.
- Loss of ability to freely provide consent through imprisonment or involuntarily incarceration
 for treatment of either a psychiatric or physical (eg, infectious disease) illness. (Note: Under
 specific circumstances and only in countries where local regulations permit, a participant who
 has been imprisoned may be permitted to continue as a participant. Strict conditions apply, and
 BMS approval is required.)
- Participant meets liver-related laboratory abnormalities (see Section 9.2.9).
- Unblinding of a participant's treatment assignment for any reason (emergency or nonemergency).
- Inability or failure to comply with protocol requirements.
- Pregnancy, positive pregnancy test, or participant no longer wishes to comply with study requirements relating to prevention of pregnancy (see Section 9.2.5).
- Participants who require initiation of an immunomodulatory agent including, but not limited to 6-MP, AZA, or biologic therapy; or who require > 3 days of treatment with higher doses of systemic corticosteroids (e.g. prednisone > 1.0 mg/kg/day for weights ≤ 40 kg or > 40 mg/day for weights > 40 kg or equivalent) will be discontinued from the study.

Reasons for discontinuation include, but are not limited to, the following:

- Physician decision: The investigator must discontinue IP if it is determined that it is not safe
 or in the participant's best interest to receive further treatment. In participants who obtain a
 pulmonology or ophthalmology consultation as outlined in Section 9.4.9 and Section 9.4.10,
 discontinuation may be recommended by the consulting physician. The Clinical Trial
 Physician or designee should be promptly notified of the decision.
- Noncompliance with IP: After consultation between the investigator, the Clinical Trial Physician or designee, and the Sponsor when appropriate, a participant may be discontinued from the study for failure to comply with dosing regimen as specified by the protocol.

- Noncompliance with protocol/protocol deviation: After consultation between the investigator, the Clinical Trial Physician or designee, and the Sponsor when appropriate, a participant may be discontinued from the study for failure to follow protocol procedures, or other event or decision that stands in contrast to the guidelines set in the protocol.
- Adverse event: A participant must be discontinued from IP if, in the judgment of the investigator or if specified in the protocol, the participant develops an AE such as an intercurrent illness or complication that justifies discontinuation of IP.

- Lack of efficacy: Decision by the participant and/or the investigator to discontinue IP due to a
 lack of expected or desired effect related to therapy or if early discontinuation criteria were
 met (see Section 5.1).
- Withdrawal by participant (or participant's parent or guardian): The participant (or participant's parent or guardian) may choose to discontinue IP at any time. The participant is expected to continue in the study and every effort should be made within the bounds of safety and the participant and their parent or guardian'schoice to have each participant complete the ET Visit and Safety Follow-up Visits. If a participant or participant's parent or guardian withdraws consent/assent, the only additional investigational data to be collected will be the follow-up of SAEs as mandated by the protocol.
- Pregnancy: If a female participant becomes pregnant, IP must be discontinued (see Section 9.2.5).
- Study termination by Sponsor
- Lost to follow-up
- Other
- For participants whose ALC level is confirmed < 200 cells/μL and permanently discontinue IP, an ET Visit should be completed. Central laboratory testing will be conducted every 14 days (± 3 days) after the ET Visit until it is above the lower limit of normal or until the ALC is considered to have stabilized and/or reached a level that is not clinically significant (see Section 9.4.12).

With the exception of participants who withdraw consent/assent or are lost to follow-up, participants who discontinue the study should complete the

Safety Follow-up Visit after the last dose for the collection of safety data and to assess their disease status. Alternative treatment for CD can be started, if needed, after the ET Visit (see Section 7.7.2 for prohibited concomitant medications within the —-day Safety Follow-up Period).

Participants who withdraw from the study will not be replaced.

Refer to Section 2 for data to be collected at the time of treatment discontinuation and follow-up and for any further evaluations that can be completed.

IM047023 Ozanimod

All participants who discontinue study intervention should comply with protocol-specified follow-up procedures as outlined in Section 2. The only exception to this requirement is when a participant withdraws consent for all study procedures, including post-treatment study follow-up, or loses the ability to consent freely (eg, is imprisoned or involuntarily incarcerated for the treatment of either a psychiatric or physical illness).

If study intervention is discontinued prior to the participant's completion of the study, the reason for the discontinuation must be documented in the participant's medical records per local regulatory requirements in each region/country and entered on the appropriate eCRF page.

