7.1 Study Interventions Administered

[figure not shown]
The label(s) for IP will include Sponsor name, address and telephone number, the protocol number, IP name, dosage form and strength (where applicable), amount of IP per container, lot number, expiry date (where applicable), medication identification/kit number, dosing instructions, storage conditions, and required caution statements and/or regulatory statements as applicable or as dictated by the site's Standard Operating Procedure. Additional information may be included on the label as applicable per local regulations.

Participants should be instructed to take the ozanimod oral dose with or without food. Instructions for administration of the pediatric dosage form (currently in development) will be provided in the Instructions for Use once available.

```
participants will continue to receive the blinded 0.46 or 0.92 mg/day adult equivalent dose

0.46 or 0.92 mg/day
```

Participants should be instructed that if they forget to take a dose, they can take the dose within 4 hours of the normal dosing time. If the participant vomits the dose, he/she should be instructed not to take another dose on the same day, but to take the next dose at the regular time on the following day.

If a single dose is missed during the first 2 weeks of treatment, or for more than 7 consecutive days during Days 15 to 28, treatment must be reinitiated using the 7-day dose escalation regimen ozanimod 0.46 mg daily for the 0.92 mg dose. If a participant misses a dose during dose escalation, the Clinical Trial Physician or designee should be contacted to discuss completing the dose escalation schedule. The missed dose and extended days for escalation need to be documented as appropriate in the eCRF.

[figure not shown]
If a participant misses more than 14 consecutive doses for any reason, the Clinical Trial Physician or designee must be contacted to discuss procedures for resuming therapy, which may include cardiac monitoring and dose escalation procedures on the first day that the participant resumes dosing.

[figure not shown]
describes cardiac monitoring procedures to be followed as indicated during dose escalation.

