7.6 Treatment Compliance

It is the investigator's responsibility to ensure that participants are correctly instructed on how to take their IP and that each participant is fully compliant with their assigned dosage regimen. Records of IP used and intervals between visits will be kept during the study. Drug accountability will be noted by the monitor during site visits and at the completion of the study. Participants will be asked to return any remaining unused IP at all visits during which IP is dispensed (except for Day) and at the end of the study. The IP should be dispensed by the investigator, or by a qualified individual under the investigator's supervision. An up-to-date treatment inventory/dispensing record must be maintained as described below.

Participants who take less than 80% or more than 120% of IP during the entire treatment period are considered non-compliant.

At each visit, previously dispensed IP will be collected by the investigator and compliance will be assessed on a participant dispensing log. Participants exhibiting poor compliance as assessed by IP counts (2 or more missed IP days in 1 week) should be counseled on the importance of good compliance to the study dosing regimen. Participants who are persistently non-compliant (< 80% or > 120%) should be discussed with the Clinical Trial Physician or designee to determine whether they should be withdrawn from the study.

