10.4.2 Primary Endpoint(s)

The primary analyses of the 2 co-primary endpoints, pediatric clinical and endoscopic remission at Week 64, will be based on the ITT population in which all will be pooled. The estimated proportions along with their associated 2-sided 95% Wald CI using a normal approximation for a single sample proportion will be constructed. Summary statistics on the number of events, sample size, and proportions for the overall group and by will also be provided.

For participants whose pediatric clinical and endoscopic remission at Week 64 cannot be adequately determined (including missing data, discontinuation, or lost to follow-up), their missing pediatric clinical and endoscopic remission will be imputed using a non-responder imputation. In addition to the primary overall analysis, a subgroup analysis will be conducted for each of A summary will be tabulated and a forest plot showing the proportions with associated 95% CIs will be produced.

Details on the analyses and the evaluations for the co-primary endpoints will be provided in the SAP, which will include comparisons with the external placebo controls as well as data from ozanimod CD adult trials.

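### Section 8.1 makes non-compliance a mandatory stop of study drug, while its own second list, Section 7.6 and Section 9 handle it by discretion or counselling

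*Combined protocol and SAP*

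**What the plan says.** Protocol Section 8.1 opens with "Participants MUST discontinue IP for any of the following reasons". One item in that list reads, in full, "Inability or failure to comply with protocol requirements". It carries no threshold, duration, judgement clause or consultation step.

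Later in Section 8.1 a second list gives reasons for discontinuation. Two of its items concern non-compliance, and both apply after consultation between the investigator, the Clinical Trial Physician and, when appropriate, the sponsor. On dosing, "a participant may be discontinued from the study for failure to comply with dosing regimen as specified by the protocol". On procedures, "a participant may be discontinued from the study for failure to follow protocol procedures".

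Section 7.6 sets two tiers for dosing. Missing study drug on two or more days within a week leads to counselling. Participants persistently outside 80% to 120% "should be discussed with the Clinical Trial Physician or designee to determine whether they should be withdrawn from the study". Section 9 (Induction and Maintenance Period) prescribes counselling for continued failure to complete the diary.

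Section 10.4.2 applies non-responder imputation to both co-primary endpoints where Week 64 status cannot be adequately determined, "including missing data, discontinuation, or lost to follow-up".

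**The concern.** A mandatory stop and a discretionary decision after consultation cannot both govern the same lapse. Read as written, a site that counsels a participant and continues dosing departs from the first list in Section 8.1. A site that stops drug at once bypasses Section 7.6 and the second list.

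Two things follow. A participant who is benefiting could be taken off drug because of a drafting conflict. The co-primary proportions could also depend to some degree on which passage a site applies. A participant stopped under the mandatory item would be assessed off drug at Week 64, or would have no Week 64 assessment and be imputed as a non-responder. The primary analysis is a single pooled proportion, and Section 10.4.2 foresees comparison with external placebo controls. No concurrent placebo arm would therefore share such a loss.

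**Working it through.** **Step 1: the passages side by side.**

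| Place | Lapse | Stated consequence |
|---|---|---|
| 8.1, first list | Any failure to comply with the protocol | Drug must be stopped |
| 8.1, second list | Non-compliance with dosing | Discontinuation possible, after consultation |
| 8.1, second list | Non-compliance with procedures | Discontinuation possible, after consultation |
| 7.6 | Two or more missed days in a week | Counselling |
| 7.6 | Persistently outside 80% to 120% | Discussion of whether to withdraw |
| 9 | Continued diary non-compliance | Counselling |

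The first row is broad enough to cover every other row. Its lack of a qualifier is not simply the style of that list: the item on participants enrolled in error depends on a safety judgement, and the item on adverse events depends on the investigator's opinion.

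**Step 2: can the rows be reconciled as drug versus study?** The first list speaks of stopping drug, while 7.6 and the second list speak of leaving the study. Section 8.2.1 keeps the two apart. One could therefore read the text as a mandatory drug stop with discretionary study withdrawal. That reading fails for two reasons. The second-list items stand under the heading for discontinuation from study intervention. Counselling on dosing also makes sense only if dosing continues.

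**Step 3: the route to the endpoint.**

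- Section 8.1.1 requires participants who stop drug to be followed for outcomes, so Week 64 data may exist, although off drug.
- Section 9 sends those who stop treatment to an early termination visit and safety follow-up visits. It makes endoscopy at the early termination visit optional.
- Section 10.4.2 imputes non-response only where status cannot be adequately determined. It names discontinuation without saying whether of drug or of study.

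Imputation is therefore possible but not automatic. It is more plausible for endoscopic than for clinical remission.

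**Step 4: scale.** Inputs from Section 10.2 are n = 100 evaluable participants, a PCDAI remission rate of 15.8% and an endoscopic remission rate of 5.8%. Section 10.4.2 specifies the 95% Wald interval.

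The plan's own precision reproduces on n = 100, with half-width = 1.96 × √(p(1 − p)/n):

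- Endoscopic: 1.96 × √(0.058 × 0.942/100) = 4.6%, giving 1.22% to 10.4%, as in Table 10.2-2.
- CDAI remission: 1.96 × √(0.217 × 0.783/100) = 8.1%, as in Table 10.2-1.

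One remitter imputed as a non-responder moves the estimate by 1/100 = 1 percentage point. PCDAI remission would go from 15.8% to 14.8%, and endoscopic remission from 5.8% to 4.8%. For k such participants the loss is k percentage points. The documents give nothing from which to estimate k.

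**The case against.** The strongest reply is that a general item should be read together with the specific rules. Section 7.6 reserves the term non-compliant for intake outside 80% to 120% over the whole treatment period and treats two missed days in a week as a lesser matter. On that view no sensible site would stop drug for a minor lapse. This is a fair account of what was probably intended. It does not remove the conflict, because even persistent non-compliance under 7.6 leads to a discussion and not to a mandatory stop, and the two lists within 8.1 still disagree.

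A reader might add Section 7.1 as a further contradiction. There, "If a single dose is missed during the first 2 weeks of treatment", and in one other stated case, "treatment must be reinitiated using the 7-day dose escalation regimen". The documents do not support that addition. A participant managed under the protocol's own missed-dose rule is arguably complying with it, so the point does not rest on 7.1.

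A reader might also infer that every participant stopped under the mandatory item becomes a non-responder. Sections 8.1.1 and 10.4.2 do not say so. The visible estimand text (Section 10.4.6.3) shows no strategy for stopping drug, but part of it may be blacked out, so its absence is not held against the plan.

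Finally, the analysis is descriptive and pooled, with no hypothesis test. Extra imputed failures would lower the ozanimod rate, which is the conservative direction against an external placebo rate. Assignment is randomised and blinded, and nothing shown suggests a difference between doses. All of this stands, and it limits the statistical weight of the point.

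**Conclusion.** The text is wrong as written, on a small scale. Section 8.1 contradicts itself, and its mandatory item contradicts Section 7.6 and the diary rule in Section 9. Sites could handle the same participant differently.

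The effect on the co-primary endpoints is conditional. It needs a site to apply the mandatory item literally, a participant who would otherwise have been in remission at Week 64, and either loss of remission off drug or a status that cannot be determined. Each remitter imputed as a non-responder costs 1 percentage point at n = 100. The enrolment target is not visible. The intent-to-treat denominator may exceed 100, and the step would then be 100/N percentage points for N participants analysed.

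It would be tempting to state an overall percentage loss. The documents give no rate of non-compliance and no indication of how many sites would read the item literally, so any such figure would be only the product of the assumptions put in. The total effect is unknown.

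**What to change.** Reconcile the mandatory item in Section 8.1 with the two non-compliance items in its second list, with Section 7.6 and with the diary rule in Section 9, so that each kind of non-compliance has one stated consequence. If stopping is to be mandatory at some point, the same threshold should appear in every place. If it is to be discretionary, the mandatory list should not contain an unqualified item. Sections 8.1 and 7.6 should cross-refer to the single rule. Which rule holds is for the sponsor to decide.

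The cost is one wording change in an amendment, with cross-references. Nothing in the planned analysis changes.
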